3.3 Rationale of dose/regimen, route of administration and duration of treatment

The ranibizumab dose used in this study as intravitreal injection (0.5 mg) was shown to be safe and effective in previous approval trials investigating VI due to DME (e.g. RESTORE study) and is approved in the EU for treatment of age related macular degeneration (AMD), visual impairment due to DME, retinal vein occlusion (RVO) and myopic choroidal

neovascularization (mCNV). The comparator arm is the standard of care and treatment is according to the current label of ranibizumab.

Initial treatment of both arms on a monthly basis until maximum BCVA and disease inactivity or no further change in disease activity is reflecting the current guidelines on how to treat DME using both functional and morphologic criteria (Stellungnahme der Deutschen Ophthalmologischen Gesellschaft, der Retinologischen Gesellschaft und des Berufsverbandes der Augenärzte Deutschlands, 2013, Bandello 2012)

The investigational arm, arm 1 (DI) is offering a treatment arm, where the investigator decides when to monitor and to treat the patient according to current visual acuity and disease activity. The rationale for this investigational arm is to find the optimal and individual treatment regimen based on the DME disease activity of each patient, reducing visits but gaining comparable VA outcome. As physicians do have experience with treatment of DME with anti-VEGF since at least 3 years we assume that this treatment arm is more realistic than complex (re-)treatments like the one investigated in the RETAIN study.

The maximum treatment duration might be 12 months in this study in both treatment arms.

As primary efficacy endpoint is BCVA local assessors are masked to the treatment assignment in order to ensure unbiased evaluation of the primary objective. To further reduce bias on secondary and exploratory objectives reading centers are blinded to treatment assignment.

3.4 Rationale for choice of comparator

PRN regimen with monthly monitoring with anti-VEGF medication based on VA and disease activity is the current standard of care for patients with VI due to DME (Stellungnahme der Deutschen Ophthalmologischen Gesellschaft, der Retinologischen Gesellschaft und des Berufsverbandes der Augenärzte Deutschlands, 2013, Bandello 2012). Also initial monthly therapy to reach maximum VA and disease inactivity or no further change in disease activity can be found in these guidelines. After this initial phase, patients will be monitored monthly and retreated if disease activity appears (e.g. impairment of VA or worsening of morphologic parameters).

3.5 Purpose and timing of interim analyses/design adaptations

Not applicable.

3.6 Risks and benefits

Clinical experience with ranibizumab in DME has been well documented by several pivotal approval studies: the Phase II RESOLVE (CRFB002D2201), and the Phase III RESTORE (CRFB002D2301), RESTORE Extension (CRFB002D2301-E1), RETAIN (CRFB002D2304), REVEAL (CRFB002D2303), and RISE (FVF4170g), and RIDE (FVF4168g) (Massin et al 2010, Mitchell et al 2011, Nguyen et al 2012, Lang et al 2013, Schmidt-Erfurth et al 2014; Brown et al. 2013; Novartis data on file) in Caucasian, Asian and Black patients. In these studies 2023 patients were randomized, of which 1051 were successfully treated up to 3 years with 10 mg/ml Ranibizumab for VI due to DME. Another major clinical trial conducted by the DRCR.net study group provided further evidence for the

efficacy and tolerability of ranibizumab for the treatment of visual impairment due to DME (DRCR.net 2010, DRCR.net 2011a, DRCR.net 2012). In this trial 375 of 691 patients were randomized to 0.5 mg Ranibizumab treatment. All mentioned trials did not show any new safety findings compared to trials in AMD.

Also several non-interventional studies include patients with visual impairment due to DME (about 3700 in studies Luminous, CRFB002A2406 and Ocean, CRFB002ADE18, effective June 2014) which are currently still recruiting.

Weighing the substantial clinical benefit achieved with ranibizumab across multiple clinical trials, such as the RESOLVE, RESTORE, RESTORE Extension, REVEAL, RIDE, RISE, DRCR.net studies, and the safety profile as observed for up to 36 months, the results of these studies support the use of ranibizumab for the treatment of patients with visual impairment due to diabetic macular edema (Ranibizumab Investigators Brochure edition 14, December 2015).

Intravitreous injections have been associated with endophthalmitis, intraocular inflammation, rhegmatogenous retinal detachment, retinal tear and iatrogenic traumatic cataract. Therefore proper aseptic injection techniques will be used and patients will be monitored to permit early treatment if an infection occurs.

Transient increases in intraocular pressure (IOP) have been seen within first hour after injection of ranibizumab. Sustained IOP increases have also been reported. Therefore, in this study pre- and post-injection IOP will be measured, reported and managed appropriately. Additionally, perfusion of the optic nerve head will be monitored as needed.

There is a potential risk of arterial thromboembolic events following intravitreal use of VEGF inhibitors. Therefore, patients with known risk factors for stroke, including history of prior stroke or transient ischemic attack will be carefully evaluated by their physicians as to whether ranibizumab 0.5 mg treatment is appropriate and the benefit outweighs the potential risk. This risk to patients in this trial will be also minimized by compliance with the inclusion/exclusion criteria and close clinical monitoring.

There are no known clinically relevant disadvantages to participate in the study.

4 Population

The study will include adult patients with Type 1 or Type 2 diabetes mellitus and visual impairment due to diabetic macular edema. A total of 130 patients (60 in each treatment arm) will be randomized at approximately 30 centers across Germany. Patients will be treated in an outpatient setting.

The calculation of the sample size is provided in Section 9.7.

4.1 Inclusion criteria

Patients eligible for inclusion in this study have to fulfill **all** of the following criteria:

Patient

1. Male or female patients > 18 years of age giving written Informed Consent and who are willing and capable to comply with all study procedures.
2. Patients with Type 1 or Type 2 diabetes mellitus with glycosylated hemoglobin (HbA1c) $\leq 12.0\%$ (107 mmol/mol) at screening (Visit 1).

Inclusion criteria for the study eye at screening:

3. Patients with visual impairment due to DME in at least one eye. If both eyes are eligible, the one with the worse visual acuity, as assessed at Visit 1, will be selected by the investigator as the study eye.
4. BCVA ≥ 24 and ≤ 78 letters in the study eye, using ETDRS-like visual acuity testing charts at a testing distance of 4 resp. 1 meters (approximate Snellen equivalent of 20/32 to 20/320) at screening.
5. Concomitant conditions in the study eye are only permitted if, they do not prevent improvement of visual acuity on study treatment

4.2 Exclusion criteria

Patients fulfilling **any** of the following criteria are not eligible for inclusion in this study. No additional exclusions may be applied by the investigator, in order to ensure that the study population will be representative of all eligible patients.

Patient Compliance/ Administrative

1. Pregnant or nursing (lactating) women, where pregnancy is defined as the state of a female after conception and until the termination of gestation, confirmed by a positive hCG test.
2. Women of child-bearing potential, defined as all women physiologically capable of becoming pregnant, unless they are using effective methods of contraception during dosing of study treatment. Effective contraception methods include:
 - Total abstinence (when this is in line with the preferred and usual lifestyle of the subject. Periodic abstinence (e.g., calendar, ovulation, symptothermal, post-ovulation methods) and withdrawal are not acceptable methods of contraception
 - Female sterilization (have had surgical bilateral oophorectomy with or without hysterectomy) or tubal ligation at least six weeks before taking study treatment. In case of oophorectomy alone, only when the reproductive status of the woman has been confirmed by follow up hormone level assessment
 - Male sterilization (at least 6 months prior to screening). For female subjects on the study, the vasectomized male partner should be the sole partner for that subject
 - Barrier methods of contraception: Condom or Occlusive cap (diaphragm or cervical/vault caps) with spermicidal foam/gel/film/cream/ vaginal suppository

- Use of oral, injected or implanted hormonal methods of contraception or other forms of hormonal contraception that have comparable efficacy (failure rate <1%), for example hormone vaginal ring or transdermal hormone contraception
- Placement of an intrauterine device (IUD) or intrauterine system (IUS)

In case of use of oral contraception women should have been stable on the same pill for a minimum of 3 months before taking study treatment.

Ocular medical history

3. Active intraocular inflammation (grade trace or above) in either eye at enrollment.
4. Any active infection (e.g., conjunctivitis, keratitis, scleritis, endophthalmitis) in either eye at the time of enrollment.
5. History of uveitis (any cause) in either eye at any time.
6. Structural damage within 0.5 disc diameter of the center of the macula in the study eye likely to preclude improvement in visual acuity following the resolution of macular edema, including atrophy of the retinal pigment epithelium, subretinal fibrosis, laser scar(s).
7. Patients with both, a BCVA score of > 73 letters and a central subfield thickness (CSFT) of < 300 µm in the study eye.
8. Uncontrolled glaucoma in either eye at screening (IOP > 24 mmHg on medication or according to investigator's judgment).
9. Neovascularization of the iris in either eye.
10. Vitreous hemorrhage impairing the adequate diagnosis of DME in the study eye
11. Evidence of clinically relevant vitreofoveal adhesion in the opinion of the investigator, vitreofoveal traction with foveal involvement or epiretinal membrane with foveal involvement in the study eye that is likely to prevent improvement of BCVA loss due to DME.
12. Proliferative vitreoretinopathy in study eye
13. History of retinal detachment, retinal tear or macular hole in the study eye.
14. Neovascularization covering an area of \geq 2 disc areas within the macula (defined as area with 6mm diameter centered on the fovea), originating either from neovascularization of the disc or multiple neovascularization's elsewhere in study eye
15. Patients who are monocular or have a BCVA score in the non-study eye (fellow eye) < 24 letters (approximate Snellen equivalent of 20/320) at Visit 1.

Prior and planned Ocular treatments

16. Any intraocular surgery in the study eye within 4 months prior to randomization.
17. Vitrectomy/vitreoretinal surgery
 - a. In the medical history or planned for study eye
 - b. planned vitrectomy or vitrectomy in last 3 months in fellow eye
18. Planned medical or surgical intervention during the 12-months study period likely to interfere with study schedule or outcomes.

19. Panretinal laser or focal/grid laser photocoagulation in the study eye within 3 months prior to randomization unless sufficient documentation of laser photocoagulation in that period of time is available.
20. Treatment with anti-angiogenic drugs (pegaptanib sodium, anecortave acetate, bevacizumab, ranibizumab, VEGF-Trap, etc.)
 - within 3 months prior to randomization for study eye
 - within 1 month prior randomization for fellow eye.
21. Use of other investigational drugs at the time of enrollment, or within 3 months or 5 half-lives from enrollment, whichever is longer.
22. History of intravitreal corticosteroid treatment in phakic study eye.
23. Intravitreal corticosteroids in post-cataract surgery study eye (aphakic or pseudophakic, without damaged posterior capsule) within 3 months or 6 months for dexamethasone implant (Ozurdex®) or 3 years for fluocinolone implant (Iluvien®) prior to randomization.
24. Ocular conditions in the study eye that require chronic concomitant therapy with topical ocular corticosteroids.

Systemic conditions or treatments

25. History of stroke within 4 months prior to enrollment.
26. Renal failure requiring dialysis or renal transplant.
27. Untreated diabetes mellitus.
28. Blood pressure systolic > 160 mmHg or diastolic > 100 mmHg at screening and randomization.
29. Conditions that require chronic concomitant therapy with systemically administered corticosteroids.
30. Current use of or likely need for systemic medications known to be toxic to the lens, retina or optic nerve, including Deferoxamine, Chloroquine/ hydroxychloroquine (Plaquenil), Tamoxifen, Phenothiazines and Ethambutol.
31. Use of any systemic anti-VEGF drugs within 3 months prior to Screening (e.g. bevacizumab [Avastin®], ziv-aflibercept [Zaltrap®]).
32. Known hypersensitivity to fluorescein or ranibizumab or any component thereof or drugs of similar chemical classes.
33. Any type of advanced, severe or unstable disease or its treatment, that may interfere with primary and/or secondary variable evaluations including any medical condition that could be expected to progress, recur, or change to such an extent that it may bias the assessment of the clinical status of the patient to a significant degree or put the patient at special risk

5 Treatment

5.1 Protocol requested treatment

5.1.1 Investigational treatment

- Ranibizumab/RFB002: 10 mg/ml solution for injection

Study medication will be supplied in commercially available packaging labeled with “Zur klinischen Prüfung bestimmt”. Each vial or pre-filled syringe (PFS) will be labeled with the appropriate information. Medication labels will comply with the legal requirements and be printed in German. The storage conditions will be described on the label. Study medication should not be stored together with commercial Lucentis® to avoid mix up.

Ranibizumab is formulated as a sterile solution aseptically filled in a sterile glass vial or PFS. Each vial or PFS contains ranibizumab in an aqueous solution (pH 5.5) with histidine, trehalose, and polysorbate 20. The vial and PFS do not contain preservatives and are suitable for single use only. Ranibizumab must be stored according to the label instructions and it must be kept in a secure locked facility.

Novartis will provide sufficient supplies of ranibizumab for treatment of the study eye to allow for completion of the treatment period.

5.1.2 Additional study treatment

Focal/grid laser can be applied additionally in both arms but earliest at month 3.

Patients with indication for PRP (e.g. PDR, large non-perfusion areas, severe non-proliferative diabetic retinopathy) will be treated with additional panretinal photocoagulation (PRP) at baseline or at least within 3 months after randomization in both arms.

Macular ischemia should not be treated with PRP according to already mentioned guidelines.

For more details please refer to chapter [5.5.3.2 Handling of other study treatment](#).

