5.3 Treatment assignment, randomization

Randomization will be done within the eCRF. Only after confirmation of the diagnosis by CRC the randomization will be possible. At visit 2 an eligible patient will be given the lowest available randomization number. This number assigns the patient to one of the treatment arms.

The randomization numbers will be generated using the following procedure to ensure that treatment assignment is unbiased and concealed from patients and investigator staff. A randomization list will be produced by or under the responsibility of Novartis Biometry using

a validated system ensuring assignment of treatment arms to randomization numbers in the specified ratio.

The randomization scheme for patients will be reviewed and approved by a member or delegate of the Novartis Biometry Randomization Group.

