9.4.2 Statistical model, hypothesis, and method of analysis

The primary objective of this trial is to demonstrate, that the ranibizumab treatment at the discretion of the investigator (DI) is non-inferior to ranibizumab PRN treatment with respect to the mean average BCVA change from baseline to month 12.

The following hypothesis will be tested at a one-sided 0.025 level.

Non-inferiority with respect to BCVA:

$H_0: \mu_{DI} - \mu_{PRN} \leq -\Delta$ versus $HA: \mu_{DI} - \mu_{PRN} > -\Delta$

where μ_{DI} and μ_{PRN} are the unknown mean average changes from baseline in BCVA to month 12 in the DI regimen and the PRN regimen, respectively. Δ is the non-inferiority margin and is pre-defined to be 4 letters (see section 3.2 for the justification of the margin).

The hypothesis testing with respect to non-inferiority of BCVA will be carried out using an analysis of covariance model including treatment group and center as factor and baseline BCVA as continuous covariate. For the treatment contrast, the point-estimate will be given with its (two-sided, 95%-) confidence interval and the p-value for the (unshifted) null hypothesis $\mu_{DI} - \mu_{PRN} = 0$. The one-sided non-inferiority-p-value for the shifted hypothesis $\mu_{DI} - \mu_{PRN} \leq -\Delta$ will be calculated additionally. Non-inferiority will be claimed, if the lower limit of the confidence interval does not exceed $-\Delta$. (Please notice that the lower limit of a 2-sided, 95% confidence interval is identical to the lower limit of a 1-sided, 90% confidence interval which is usually used to assess non-inferiority).

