9.7 Sample size calculation

A sample size of 133 patients per treatment arm will have 90% power to establish non-inferiority at a margin of 4 letters for the 0.5 mg ranibizumab “at investigators discretion” dosing regimens in comparison to 0.5 mg ranibizumab PRN in the mean average change in BCVA based on a one-sided 0.025 significance level, assuming a treatment difference of 0 letters, a standard deviation of 10 letters and an underlying normal distribution for an unstratified t-Test (nQuery Advisor 7.0).

The Phase III study (RESTORE) results in the FAS suggest a mean average change in BCVA of 6 letters with a standard deviation of about 7-8 letters for ranibizumab. To account for some more variability related to the retreatment concepts and subgroup treated with additional PRP laser in this study as compared to RESTORE, a standard deviation of 10 letters is assumed. To account for some drop outs 150 patients will be randomized per treatment arm.

Due to reasons mentioned in section “Summary of protocol amendments” recruitment will be terminated, resulting in a reduced sample size present for analysis.

As a consequence results are to be interpreted in a purely descriptive manner. With an estimate of about 120-150 patients to be enrolled by end of recruitment the expected power would be about 55-60% and will be evaluated accordingly.

10 Ethical considerations**10.1 Regulatory and ethical compliance**

This clinical study was designed and shall be implemented and reported in accordance with the ICH Harmonized Tripartite Guidelines for Good Clinical Practice, with applicable local regulations (including European Directive 2001/20/EC, US Code of Federal Regulations Title 21, and Japanese Ministry of Health, Labor, and Welfare), and with the ethical principles laid down in the Declaration of Helsinki.

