## 2.6.2 Statistical hypothesis, model, and method of analysis

As a consequence of the early recruitment termination, all analyses will be interpreted in a purely descriptive manner. Nevertheless, the planned non-inferiority hypothesis testing of the ranibizumab injections at the discretion of the investigator (DI) and ranibizumab injections of current standard care (PRN) for patients with DME will still be performed.

The following hypotheses related to non-inferiority at a one-sided 0.025 significance level will be performed:

Null hypothesis:  $H_0: \mu_{DI} - \mu_{PRN} \leq -\Delta$

Alternative hypothesis:  $H_A: \mu_{DI} - \mu_{PRN} > -\Delta$

where  $\mu_{DI}$  and  $\mu_{PRN}$  are the unknown mean visit-averaged change from baseline in BCVA from month 1 to EoT, in the DI regimen and the PRN regimen, respectively.  $\Delta$  is the non-inferiority margin and is predefined to be 4 letters. The hypothesis testing with respect to non-inferiority of BCVA will be carried out using an analysis of covariance (ANCOVA) model including study treatment (DI, PRN) and center as factors and baseline BCVA as continuous covariate.

The Least Square (LS) (“adjusted”) means for each treatment arm and estimates of the difference (DI - PRN) will be given along with the respective two-sided, 95% CI and the p-value for the (unshifted) null hypothesis ( $\mu_{DI} - \mu_{PRN} = 0$ ).

The one-sided non-inferiority p-value for the shifted hypothesis ( $\mu_{DI} - \mu_{PRN} \leq -\Delta$ ) will be calculated. Non-inferiority will be claimed, if the lower limit of the two-sided 95% CI (equivalent to the one-sided 97.5% CI) does not exceed  $-\Delta$  (i.e. -4 letters).

There are no multiplicity issues as there is only one primary comparison.

The key assumptions that underlie the use of ANCOVA model for the primary analysis will be checked. The normality assumption of the error term will be performed and in case of clear deviations, a non-parametric comparison – Wilcoxon Rank Sum Test – will be performed instead of ANCOVA for the primary analyses. Homogeneity of variance between/ among treatment arms will be evaluated visually.

At each visit, descriptive statistics will be provided for the following values of the primary efficacy variable BCVA by visits and treatment arms:

- Baseline
- Absolute and change from baseline
- Visit-averaged change from baseline in BCVA from month 1 to EoT

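### The PRP subgroup is one stated reason for the SD of 10 letters, yet no planned DI - PRN comparison adjusts for the baseline retinopathy status behind it; adding this term is a cheap efficiency gain, not the repair of an error

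*Protocol*

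**What the plan says.** - **Who gets PRP.** Protocol 5.1.2: "Patients with indication for PRP (e.g. PDR, large non-perfusion areas, severe non-proliferative diabetic retinopathy) will be treated with additional panretinal photocoagulation (PRP) at baseline". The sentence goes on to allow PRP within three months after randomization, in both arms. Protocol 5.5.3.2.2 repeats this.
- **Why the SD is 10.** Protocol 9.7 cites an SD of about 7-8 letters from the earlier phase III ranibizumab trial and raises it: "To account for some more variability related to the retreatment concepts and subgroup treated with additional PRP laser in this study". SAP section 3 repeats the reasoning. Two sources are named, with no split between them.
- **What is graded at entry.** SAP 2.4.3 lists, from the central reading center, the baseline DRS grade of the study eye (with a post-panretinal-laser, not gradable level), signs of panretinal laser, and the presence and extent of capillary non-perfusion.
- **Randomization.** Protocol 5.3: "At visit 2 an eligible patient will be given the lowest available randomization number". No stratification factor is described.
- **Primary model.** SAP 2.6.2: "model including study treatment (DI, PRN) and center as factors and baseline BCVA as continuous covariate". Protocol 9.4.2 and SAP Table 5-3 have the same terms.
- **Other models.** The MMRM in SAP 2.6.4 adds visit terms only. The extended ANCOVAs in SAP 2.8.2 add changes in HbA1c, blood pressure and lipids. Need for PRP appears only in the separate subgroup and descriptive summaries of SAP 2.2.1 and 2.6.4.
- **Status of the test.** SAP 1.1 calls all analysis exploratory, but SAP 2.6.2 still runs the non-inferiority test and states a rule for claiming it.

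**The concern.** The sponsor names a subgroup as a source of extra variance in the primary endpoint. Membership depends largely on a condition that masked readers grade before treatment starts. If such eyes gain fewer or more letters on average than the rest, that difference sits in the error term of the primary model, although one extra factor would remove it. Recruitment stopped at 135 patients against 300 planned, so precision is scarce. A covariate picked after unmasking would carry little weight, so the choice has to be made beforehand. The PRP summaries do not fill the gap. They do not adjust the treatment contrast, and they group by need for PRP, which unmasked physicians may act on after randomization.

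**Working it through.** **Inputs from the documents.** Margin 4 letters; one-sided 0.025 ("The following hypothesis will be tested at a one-sided 0.025 level", Protocol 9.4.2); Protocol 9.7: "assuming a treatment difference of 0 letters, a standard deviation of 10 letters and an underlying normal distribution for an unstratified t-Test". 135 patients randomized 1:1 (SAP 1.1), so 67.5 per arm on average.

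**Inputs assumed.** Share p of eyes with a PRP indication, and mean gap d in visit-averaged BCVA change between those eyes and the rest, net of center and baseline BCVA. The documents give neither. I use p = 30% and d = 3-5 letters, and show wider values.

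**Step 1: reproduce the plan's figure.** "A sample size of 133 patients per treatment arm will have 90% power". Normal approximation: n = 2 × (1.960 + 1.282)² × 10² / 4² = 131.4, rounded up to 132. The noncentral t gives 89.93% power at 132 and 90.15% at 133. The stated 133 is right.

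**Step 2: power at 135 patients.** SE = 10 × √(2/67.5) = 1.72 letters. Power = Φ(4/1.72 − 1.96) = 64.2% (noncentral t: 63.6%). The plan quotes 55-60% for 120-150 patients; the t-test gives 58.4% at 120, 63.6% at 135 and 68.2% at 150, before dropouts. The gain in Step 3 hardly depends on this. At 60 per arm, power goes from 59.1% to Φ(4/(9.91 × √(2/60)) − 1.96) = 59.9% for d = 3, and to 61.4% for d = 5 (SD 9.73).

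**Step 3: effect of the covariate.** A binary factor explains p(1−p)d² of the variance of 100, so the residual SD is √(100 − p(1−p)d²). With p = 0.3 and 67.5 per arm (normal approximation):

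| Gap d | Variance explained | Residual SD | Power | 95% CI half-width | n per arm for 90% |
|---|---|---|---|---|---|
| 0 | 0% | 10.00 | 64.2% | 3.37 | 132 |
| 3 | 1.9% | 9.91 | 65.0% | 3.34 | 129 |
| 5 | 5.3% | 9.73 | 66.5% | 3.28 | 125 |
| 10 | 21.0% | 8.89 | 74.4% | 3.00 | 104 |

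For d = 3-5 over shares of 10-50%, power is 64.6% to 67.0%, a gain of 0.4 to 2.8 points.

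**Step 4: ceiling.** If the factor removed the whole SD increase, back to 8 or 7, power would be 82.8% or 91.3%. At p = 0.3 that needs d = √(36/0.21) = 13.1 or √(51/0.21) = 15.6 letters.

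**Step 5: is chance imbalance a separate harm?** Its contribution to the estimate has SD d × √(2p(1−p)/67.5), which is 0.39 letters at p = 0.3, d = 5. On the half-width scale this is 1.96 × 0.39 = 0.77, and √(3.28² + 0.77²) = 3.37, the unadjusted half-width. Imbalance is what widens the interval from 3.28 to 3.37; it is not an extra harm.

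**Step 6: cost.** With about 30 centers (Protocol section 4), the planned ANCOVA leaves about 135 − 30 − 1 − 1 = 103 residual degrees of freedom. A three-level factor takes 2.

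**The case against.** The strongest reply is that nothing here is wrong with the plan. Center and baseline BCVA are a conventional covariate set. Protocol 9.7 speaks of variability and never says that PRP-indicated eyes differ in mean change. A main effect removes only a mean difference, so extra spread within the subgroup, or spread from the retreatment concepts, would remain. The named source is PRP treatment, which may be given after randomization. All results are exploratory, baseline DRS is tabulated by arm so an imbalance would be visible, and replacing the protocol's primary model after recruitment closed needs a good reason.

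Most of this stands, and it rules out three stronger readings.

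- A reader might infer that the plan knowingly leaves avoidable noise in the contrast. The documents show only that the noise may be avoidable.
- A reader might infer that unstratified imbalance biases the estimate. Under randomization it does not, and Step 5 shows that the interval already contains it.
- A reader might infer that adjustment could restore the precision of the earlier trial. That needs a 13-16 letter gap at a 30% share. Even a 10-letter gap, around the 6-letter mean change cited in Protocol 9.7, implies group means of about −1 and 9 letters (or 3 and 13 if the indicated eyes do better). No passage supports that.

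Two parts do not stand. The exploratory label does not settle the matter, because SAP 2.6.2 keeps the test and a claim rule. And a visible imbalance in a baseline table does not show what it does to the DI - PRN estimate; an adjusted analysis does.

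**Conclusion.** The point holds as an efficiency suggestion. The plan names the PRP subgroup as a variance source, has the indications graded centrally at baseline, and does not use those grades in any public analysis of the treatment contrast. The likely gain is small: 0.8 to 2.3 power points at an assumed 30% share and a 3-5 letter gap, and zero if the subgroup differs only in spread.

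The estimate rests on an SD of 10 with no credit for center or baseline BCVA, on the assumed share and net gap, and on a factor that captures the indication without misclassification. A DRS-only factor would place mild or moderate NPDR eyes with large non-perfusion in the wrong level and lose part of the gain. What favors acting is the cost, which is close to nothing while the data are still masked.

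**What to change.** Before unmasking:

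1. In SAP 2.6.2 or 2.6.4, and in Table 5-3, add an ANCOVA on the FAS (LOCF) with treatment, center, baseline BCVA and the centrally graded baseline retinopathy status of the study eye. Suggested levels: mild or moderate NPDR without large capillary non-perfusion; severe NPDR, PDR or large non-perfusion; status post panretinal laser or not gradable.
2. State how the graded extent categories in SAP 2.4.3 define large non-perfusion for this factor, and how missing grades are assigned.
3. Use baseline grades only, never PRP received after randomization.
4. Repeat the model for the PPS and add the factor to the MMRM.
5. Report it beside the protocol model: either as primary with the protocol model as sensitivity, or at minimum as a pre-specified supportive analysis. Because the gain may be zero, the supportive role is enough.
6. Record the addition in SAP section 4, which now states that nothing was changed.

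Cost: SAP wording, one model term, about 2 degrees of freedom and a rule for ungradable eyes. No new data are needed.
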